----------------------	---

Reference Therapy	Subjects in Phase I who are randomized to sham treatments will have schedules, systematic assessments, and treatment approaches that are identical to subjects randomized to active treatments. Subjects, treaters, and clinical raters will not know whether the treatment is active or sham in nature (double-blinded). The sham coil is identical in its appearance to the active coil. Furthermore, Neuronetics, Inc. has created an acoustic matching profile that renders the sensory experience of the treatments virtually indistinguishable to subjects or researchers. The acoustic signal creates a painless percussive sensation that will be felt by the subject and will assist in simulating the active condition.
Concomitant Therapy	
Permitted: Subjects are expected to be on stable dose pharmacotherapy with one of the antidepressants listed in protocol Section 4.1 (Inclusion Criteria). Any other medication change including initiation, discontinuation, or dose adjustment of medication, needs to be discussed with the site PI and approved before implementation.
 
Prohibited: Initiation of medication listed in protocol Section 4.2 (Exclusion Criteria) is not permitted during either phase of the study. Dose adjustment or initiation of permitted medications (Section 4.1 Inclusion Criteria) after enrollment must be approved by the site PI prior to implementation.

Statistical Methodology	
Statistical analysis plan for objectives 1, 2a, 2b : Treatment outcomes defined as remission, response, or nonresponse will be assessed using a logistic regression model with independent variables of treatment number (i.e. #10 vs. #20 vs. #30) and gender (male vs. female) will be analyzed at the 0.05 significance level. The primary outcome measures will include the CDRS-R and CGI-I.
 
Statistical analysis plan for objective 3 (data from MCR site only): The hypotheses will be tested using t-tests. Additionally, analyses of covariance will be performed to control for potentially important covariates or confounders, such as age or gender. Non-parametric distribution will be analyzed by non-ANOVA statistics.

1 Introduction

This document is a protocol for a human research study. This study will be carried out in accordance with the procedures described in this protocol, applicable United States government regulations, Mayo Clinic of Rochester (MCR), and the Medical University of South Carolina (MUSC) policies and procedures.

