3.2 Primary Study Endpoints

3.2.1 Phase I

Primary outcome screening measures in Phase I will be assessed at 10-treatment intervals which will equate to roughly every other week until the 30th treatment has been completed (see Table 4 for schedule of assessments). These outcome measures will provide an opportunity for mood ratings in the form of self-assessment (QIDS-A17-SR), a semi-structured clinical interview of the adolescent with input from parents (CDRS-R), and a clinical rating by the clinician of illness severity and improvement (CGI-S & I).

Furthermore, from a safety standpoint, suicidality will be carefully monitored on a weekly basis via the C-SSRS. Board certified/board eligible child and adolescent psychiatrists will administer all diagnostic assessments and clinical interviews determining study eligibility. Outcome measures assessing neurocognitive safety [the Children's Auditory Verbal Learning Test version 2 (CAVLT-2) and the Delis-Kaplan Executive Function Scale (D-KEFS)] will occur at baseline and at treatment completion and will be administered by trained psychometrists. These measures will be used in the assessment of any unanticipated change in cognitive function that may have occurred during the course of treatment. Inter-rater reliability exercises will be conducted for the CDRS-R to ensure intra-site and inter-site consistency of depression ratings.

3.2.2 Phase II, Arm 1

The schedule of primary outcome measures for Acute Treatment (Arm 1) of Phase II will be identical to that of Phase I with the exception that the End of Phase I assessments will be used for Phase II Baseline measures. See Table 5 for schedule of assessments.

3.2.3 Phase II, Arm 2

Primary outcome measures for Maintenance Treatment (Arm 2) in Phase II, including QIDS-A17-SR, CDRS-R, CGI-I, and CGI-S, will be assessed monthly. Suicidality will be carefully monitored on a monthly basis or more frequently as needed using the C-SSRS. Neurocognitive safety outcome measures (CAVLT-2 and D-KEFS) will be assessed at the completion of the maintenance treatments and at six-month follow-up. These will be

compared to Phase I Baseline and Phase I Completion assessments. See Table 6 for schedule of assessments.

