7.1 Sample Size Determination

Preliminary data from the 2011 Wall et al. pilot study[1] was used to estimate the sample size needed per treatment group to achieve at least 80% power for detecting a difference between the active and sham treatments using 2 versions of the CDRS-R depression inventory measured at baseline and completion of 30 sessions including: 1) the rate of those responding to treatment based on a CDRS-R and CGI-I finite cutoff score (binary), and 2) the raw change in CDRS-R score from baseline (continuous).

For the binary response we observed a success rate of 71% in our preliminary study. For sample-size purposes we hypothesize a success rate of 65% for rTMS. We further hypothesize a success rate of 25% for the Sham group. Based on these assumptions, we have determined that a total sample-size of N=70 (35 per group) will provide statistical power (two-tailed, alpha=0.05) of 94% to detect a difference between groups.

When the change in CDRS-R was quantified using a continuous variable we observed a mean delta of 33.3 with corresponding standard deviation of 7.3. Under the conservative assumption that the “true” standard deviation of this response is 10.0, we have determined that a total sample-size of N=70 (35 per group) will provide statistical power (two-tailed, alpha=0.05) of 91% to detect a difference between groups of 8.0 units.

Thus a total sample-size of N=35 per group will provide adequate statistical power. Since the primary analysis will be performed using the approach of LOCF, we will not adjust the sample-size to account for attrition. We will however, perform supplementary analyses which are restricted to subjects who complete the study. Under the assumption that the attrition rate is approximately 30% we repeated the power analyses described above using an effective sample-size of N=50 (25 per group). Using these effective sample-sizes, the supplemental

analysis restricted to study completers will have statistical power of 83% to detect the hypothesized difference when change in CDRS-R is quantified as a binary response and statistical power of 80% to detect a difference between groups of 8.0 units when the change in CDRS-R is quantified as a continuous variable.

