Treatment outcomes for both phases will be defined as response (CDRS-R raw score <28 & CGI-I ≤2 & CGI-S ≤2), or nonresponse (CDRS-R raw score ≥28 and CGI-I ≥3) assessed using a logistic regression model with independent variables of treatment number (i.e. #10 vs. #20 vs. #30) and gender (male vs. female) will be analyzed. Assessing potential gender effects will be a secondary analysis. The primary analysis will not adjust for gender. Although we anticipate that more females than males will participate in the study, we assume that the distribution of gender will be similar between treatment arms and have no a priori reason to suspect that the efficacy of treatment will be gender specific.

Serious adverse events will be reported as noted within the application. All adverse events will be summarized according to treatment groups. Given the sample size for the current study, the statistical power for detecting differences between groups is limited. However, we will compare between groups using an exact test.

All statistical tests will be performed at the 0.05 significance level.

Secondary Hypotheses (for MCR site only):

Baseline glutamate, reported as a CSF-corrected absolute concentration and as an overlapping resonance with glutamine, will be significantly higher in both AC and L-DLPFC in depressed adolescents as measured by ^1H -MRS at 3T when compared to data derived from previously scanned healthy controls.

In comparison to non-remission subjects, depressed adolescents treated with rTMS who achieve remission (defined as a CDRS-R raw score <28 and CGI-I ≤ 2 and CGI-S ≤ 2 at treatment completion) will exhibit a greater decrease in glutamine, reported as a CSF-corrected absolute concentration percent change (baseline to endpoint) in AC and L-DLPFC as measured by ^1H -MRS at 3T.

The hypotheses will be tested using t-tests. Additionally, analyses of covariance will be performed to control for potentially important covariates or confounders, such as age or gender. Non-parametric distribution will be analyzed by non-ANOVA statistics.

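### The only efficacy model named uses treatment number (#10, #20, #30) as a predictor, gives no method for correlated outcomes within a subject, and does not match the single post-30 endpoint that was powered

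*Combined protocol and SAP*

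**What the plan says.** Section 7.2 (Statistical Methods) classes each subject as a responder or nonresponder and says that this will be "assessed using a logistic regression model with independent variables of treatment number (i.e. #10 vs. #20 vs. #30) and gender (male vs. female"). The Statistical Methodology row of the Study Summary gives the same model for objectives 1, 2a and 2b at the 0.05 level: outcomes "will be assessed using a logistic regression model with independent variables of treatment number (i.e. #10 vs. #20 vs. #30") and gender. Objective 1 is the active versus sham comparison. No other model for efficacy is named.

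Section 3.2.1 sets the schedule: "Primary outcome screening measures in Phase I will be assessed at 10-treatment intervals", up to the 30th treatment. Table 4 and sections 6.2.4, 6.2.6 and 6.2.8 agree.

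Section 7.1 bases the sample size on outcomes "measured at baseline and completion of 30 sessions", in a binary and a continuous version. On missing data it says "Since the primary analysis will be performed using the approach of LOCF", and on that ground it does not raise the sample size for attrition.

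Section 7.2 also says "The primary analysis will not adjust for gender"; gender effects are a secondary analysis. It calls the Phase II analysis exploratory and mainly descriptive. Neither the Study Summary nor sections 7.1 to 7.3 mention generalized estimating equations (GEE), a random effect, a robust variance or any other allowance for repeated outcomes.

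**The concern.** Treatment number varies within a subject, not between subjects. For it to be a predictor, the data set must hold a separate record for each of #10, #20 and #30, so up to three per subject. A subject's response status at these three points will be correlated, and carrying a last observation forward copies an earlier status into later records. The model-based standard errors of a logistic regression are valid only if the records are independent given the predictors.

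Two things are at stake. First, if the model is run as described, the nominal 0.05 level is not the real error rate. Subject-level terms are tested too liberally and treatment-number contrasts too strictly. As written, the only subject-level term is gender. The model has no arm term, so one must be added before it can address objective 1, and arm would then have the same fault.

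Second, the powered endpoint and the named model are different analyses. If the text does not settle which is primary, the choice could be made after the data are seen.

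**Working it through.** **1. The plan's own power figures.** Inputs from section 7.1: response 65% versus 25%; difference 8.0 units with SD 10.0; two-sided alpha 0.05; 35 per group, or 25 per group for completers.

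Binary, pooled z test: power = Φ[(0.40 − 1.96·√(2·0.45·0.55/n)) / √((0.65·0.35 + 0.25·0.75)/n)].
- n = 35: (0.40 − 1.96·0.1189)/0.1089 = 1.53, power 93.7% (stated 94%).
- n = 25: (0.40 − 1.96·0.1407)/0.1288 = 0.96, power 83.2% (stated 83%).

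Continuous, noncentrality 0.8·√(n/2):
- n = 35: 91.0% by the t distribution, 91.7% by the normal (stated 91%).
- n = 25: 79.1% by t, 80.7% by the normal (stated 80%).

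The figures reproduce with one outcome per subject and no repeated-measures element.

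**2. Which data set each section needs.** Section 7.1 needs one record per subject, at #30. The model in 7.2 and the Summary needs records at #10, #20 and #30. With #30 records alone, treatment number takes a single value and cannot be a predictor. One data set cannot serve both descriptions.

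**3. Size of the distortion if the records are stacked and the correlation is ignored.** The correlation ρ between a subject's outcomes is not in the documents. I assume it equal for all pairs of time points and show 0.2 to 0.8. With m = 3 records per subject and similar response rates at each time point, the approximate ratios of true to model-based standard error are:
- subject-level term (gender, or arm if added): √(1 + (m − 1)ρ) = √(1 + 2ρ);
- contrast between two treatment numbers: √(1 − ρ).

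The real level of a nominal 0.05 test is 2·[1 − Φ(1.96/ratio)].

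| Assumed ρ | Ratio, subject-level | Real level | Ratio, treatment number | Real level |
|---|---|---|---|---|
| 0.2 | √1.4 = 1.18 | 9.8% | √0.8 = 0.89 | 2.8% |
| 0.5 | √2.0 = 1.41 | 16.6% | √0.5 = 0.71 | 0.6% |
| 0.8 | √2.6 = 1.61 | 22.4% | √0.2 = 0.45 | below 0.1% |

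At ρ = 0 both ratios are 1 and nothing is wrong.

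**4. Check by simulation.** 70 subjects, 35 per arm, about two thirds female, three binary outcomes each with a 25% response rate at every time point (an assumption), no true effects, arm term added, 1,500 runs per setting. The treatment-number contrast is #30 versus #20.

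| Mean ρ | Arm | Gender | Treatment number | Same three, clustered on subject |
|---|---|---|---|---|
| 0.00 | 5.1% | 5.3% | 5.3% | 5.5%, 5.9%, 4.7% |
| 0.31 | 12.2% | 12.1% | 1.8% | 5.3%, 4.6%, 4.6% |
| 0.47 | 15.6% | 16.1% | 0.7% | 5.1%, 4.7%, 5.7% |
| 0.78 | 22.3% | 21.8% | 0.1% | 4.6%, 4.3%, 4.7% |

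The simulation agrees with the formulas, and clustering on subject brings the error rate back to about 5%.

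**The case against.** The strongest reply is that the plan never commits to the faulty analysis. It does not say that the regression is ordinary or that records are treated as independent; in this sentence, independent variables simply means predictors. GEE and mixed logistic models are also logistic regressions. Section 7.1, with its endpoint after 30 sessions, two-group power calculation and last observation carried forward, points to one record per subject, where the problem does not arise.

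Part of this stands. It is an omission, not a stated error, and the invalid standard errors depend on how the model is fitted. But section 7.1 names no test, and its endpoint cannot be analysed with the predictor that 7.2 lists. The single-endpoint reading therefore contradicts the named model and does not explain it.

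A reader might also infer that the plan's active versus sham p-value is anticonservative. The documents do not support that: the written model has no arm term and yields no such p-value. The inflation reaches arm only if an arm term is added and clustering is still ignored. Nor is every standard error too small, since those for treatment-number contrasts err the other way. Gender is secondary, Phase II is exploratory, and the continuous change in CDRS-R is not covered by this model at all.

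**Conclusion.** The point holds as a gap and a mismatch in the plan. The one efficacy model named implies up to three correlated outcomes per subject, says nothing about that correlation, and differs from the endpoint that was powered. Run literally, a nominal 5% test would have a real level of about 10% to 22% for a subject-level term, and from about 3% to below 0.1% for a treatment-number contrast.

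Those sizes rest on an assumed common correlation of 0.2 to 0.8 and similar response rates across time points. The documents give neither the correlation nor the rates at #10 and #20. That the standard errors would be wrong needs only a nonzero correlation. The four stated powers (94%, 91%, 83%, 80%) are unaffected.

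**What to change.** In section 7.2 and the Statistical Methodology row of the Study Summary, state the primary binary analysis as active versus sham response at #30, one record per subject. This matches section 7.1.

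If #10, #20 and #30 are also to be modelled jointly, name the method: GEE or mixed logistic regression clustered on subject, with arm, treatment number and their interaction, and with standard errors corrected for the small number of subjects. Report the arm contrast at #30 from that model. The secondary gender analysis should follow the same rule if it uses more than one record per subject.

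The cost is wording only, with no change to sample size or data collection. Confidence intervals for subject-level terms will be wider than a stacked fit that ignores clustering would give.

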7.2 Statistical Methods

Descriptive Statistics

Univariate descriptive statistics and frequency distributions will be calculated as appropriate for all variables. Baseline values for demographic, clinical, and outcome variables (primary and secondary) will be tabulated for the treatment groups. These analyses will help identify potential confounding variables to be used as covariates in sensitivity analyses. Distributions across subgroups used in randomization will be compared to assess whether the randomization was successful in equalizing distributions of these prognostic variables across treatment groups.

Statistically significant differences on overall comparisons will be explored using multiple pairwise comparisons of each of the (treatment) groups using Bonferroni correction for multiple comparisons. Mean scores and standard deviation for each group will be calculated.

Subsequent multiple comparisons via Tukey's procedure will be set at 0.01 to control Type I error rate.

Primary Hypotheses:

- 1) Adolescents in Phase I treated with active rTMS at the left dorsolateral prefrontal cortex (L-DLPFC) will have significant mood improvement when compared to sham treatment.
- 2) Adolescents in Phase II treated with maintenance rTMS at the L-DLPFC will achieve sustained response of the depressive symptoms.

Phase II represents a proof of concept/preliminary study of long-term maintenance for treatment responders (either active or sham in Phase I) and an opportunity for open-active treatment in nonresponders. The inclusion of phase II is ethically necessary to ensure that all pediatric participants are offered an opportunity to receive active treatment if unresponsive in phase I. The analysis of data collected as part of phase II is exploratory and will include primarily descriptive statistics.

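### Phase I has two powered outcomes and no named deciding one; the logistic model omits treatment arm, CDRS-R change has no between-arm analysis, and the response rule leaves cases unclassified

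*Combined protocol and SAP*

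**What the plan says.** Section 7.1 sizes the trial on two outcomes measured at baseline and after 30 sessions: a binary response built from CDRS-R and CGI-I cutoffs, and the raw change in CDRS-R. At 35 per arm and two-tailed 0.05 it gives 94% power for the first and 91% for the second. It then refers to a primary analysis by LOCF without saying which outcome that is. Section 7.3 likewise speaks of one primary outcome without defining it. The synopsis says the primary measures include CDRS-R and CGI-I. Section 3.2.1 lists four scales, rated every 10 treatments.

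Hypothesis 1 in Section 7.2 is that subjects on active rTMS "will have significant mood improvement when compared to sham treatment". The model given, in almost the same words in the synopsis, is a "logistic regression model with independent variables of treatment number (i.e. #10 vs. #20 vs. #30) and gender (male vs. female"). Section 7.2 adds "The primary analysis will not adjust for gender" and "All statistical tests will be performed at the 0.05 significance level".

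Section 7.2 defines the outcome as "response (CDRS-R raw score <28 & CGI-I ≤2 & CGI-S ≤2), or nonresponse (CDRS-R raw score ≥28 and CGI-I ≥3"). The same section uses the same three cutoffs for "remission (defined as a CDRS-R raw score <28 and CGI-I ≤ 2 and CGI-S ≤ 2 at treatment completion"), whereas the synopsis lists remission and response as separate outcomes. Sections 3.1 and 6.3 define response by CDRS-R and CGI-I alone, with nonresponse as the complement.

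On multiplicity, Section 7.2 offers "multiple pairwise comparisons of each of the (treatment) groups using Bonferroni correction for multiple comparisons" and "Subsequent multiple comparisons via Tukey's procedure will be set at 0.01 to control Type I error rate".

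**The concern.** Each test on its own holds 5%. The difficulty comes when the two are read together. If response is significant and CDRS-R change is not, or the reverse, the plan does not say whether Phase I succeeded. A reading in which either win suffices, or in which the outcome is picked after the results, would raise the error above 5%, and nothing in the text excludes it.

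The comparison the trial exists to make is also not written down for either outcome. Treatment number is defined in the parenthesis as the session count (10, 20 or 30), not as arm. Once gender is dropped from the primary analysis, session count is the only listed term left. The t-tests and ANCOVA in Section 7.2 belong to the single-site spectroscopy hypotheses (the synopsis ties them to objective 3), and the exact test is for adverse events.

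Finally, a binary analysis cannot be run on subjects who are neither responders nor nonresponders.

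**Working it through.** **1. The plan's own power figures.** Inputs from Section 7.1: 65% vs 25% response; difference 8.0, SD 10.0; two-sided 0.05; 35 per arm, or 25 per arm for completers.

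- Binary, normal approximation, pooled variance under the null: power = Φ{[0.40 − 1.96·√(2·0.45·0.55/35)] / √[(0.65·0.35 + 0.25·0.75)/35]} = Φ[(0.40 − 0.2331)/0.1089] = Φ(1.533) = 93.7% (stated 94%). At 25 per arm: 83.2% (stated 83%).
- Continuous, two-sample t-test, noncentrality (8/10)·√(35/2) = 3.35: 91.0% (stated 91%). At 25 per arm: 79.1% (stated 80%; a normal approximation gives 80.7%).

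The stated figures reproduce. Exact power of a logistic test of arm at 65% vs 25%, 35 per arm, is 92.5% (Wald) or 93.3% (likelihood ratio), so putting arm in the model keeps the stated 94% within 2 points.

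**2. Error and disagreement with two tests.** The documents give no correlation r between the two test statistics. I assume r = 0.5 to 0.8 and show independence alongside. The statistics are treated as bivariate normal, each tested at ±1.96. With no effect, P(both) = 5% + 5% − P(at least one). Under the Section 7.1 effects the z-means are 1.96 + 1.53 = 3.49 and 1.96 + 1.34 = 3.30, matching the powers above.

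| r | No effect: at least one | No effect: both | Both effects true: both significant | Both effects true: exactly one |
|---|---|---|---|---|
| 0 | 9.75% | 0.25% | 85.3% | 14.2% |
| 0.5 | 9.07% | 0.93% | 86.9% | 11.0% |
| 0.7 | 8.35% | 1.65% | 87.9% | 8.8% |
| 0.8 | 7.81% | 2.19% | 88.7% | 7.4% |

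A simulation of null trials at 35 per arm, with response generated by dichotomising a variable correlated with the change score, gave 7.4–9.5% for at least one rejection as the assumed correlation ran from 1 down to 0.

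Splitting alpha at 0.025 each would give 89.0% (binary) and 85.2% (change) at 35 per arm. In a fixed sequence the first outcome is tested at the full 0.05 and keeps its stated power.

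**3. The response rule.** All combinations of the three cutoffs:

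| CDRS-R | CGI-I | CGI-S | Section 7.2 | Section 3.1 |
|---|---|---|---|---|
| <28 | ≤2 | ≤2 | response | response |
| <28 | ≤2 | ≥3 | unclassified | response |
| <28 | ≥3 | ≤2 | unclassified | nonresponse |
| <28 | ≥3 | ≥3 | unclassified | nonresponse |
| ≥28 | ≤2 | ≤2 | unclassified | nonresponse |
| ≥28 | ≤2 | ≥3 | unclassified | nonresponse |
| ≥28 | ≥3 | ≤2 | nonresponse | nonresponse |
| ≥28 | ≥3 | ≥3 | nonresponse | nonresponse |

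Section 7.2 gives 1 response, 2 nonresponse and 5 unclassified. Section 3.1 gives 2, 6 and 0.

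**4. The multiplicity sentences.** The Bonferroni sentence covers pairwise comparisons of groups. Phase I has two arms and so one pair, which leaves nothing to correct. The Tukey sentence does not name its comparisons. Neither is said to cover the two outcomes.

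**The case against.** The text leans towards binary response as primary. Section 7.1 lists it first and calls the pair two versions of one instrument, Section 7.2 and the synopsis model it, the remark about the primary analysis follows that model, and Section 7.3 uses the singular. On that reading the continuous calculation is supporting material and no second confirmatory test exists to inflate anything. The lean is real, but nowhere is it turned into a designation, and the synopsis and Section 3.2.1 point to wider lists.

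The missing arm term is very probably a drafting slip. The synopsis writes one model for objectives 1, 2a and 2b, and the Phase II arms have no sham group; the hypothesis and the power statements both imply an arm comparison. That is accepted, but a plan has to state its deciding test, and the omission occurs in both places.

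The study is labelled a pilot. However, Section 7.1 powers Phase I for an arm comparison, and Section 7.2 calls only the Phase II analysis exploratory.

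Three limits stand. The 5 of 8 counts combinations, not subjects; some need discordant ratings, and the documents give no frequencies. An assumed correlation of 0.8 is about the most that dichotomising a normal variable allows (0.73 at 25% response, 0.80 at 50%), so the lower end of the error range is the less plausible one. And early-withdrawal ratings (Section 6.2.8, Table 4 footnote g) will supply a CGI-I for most dropouts. Section 6.2 does let subjects decline some assessments, so a few could still have none to carry forward.

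**Conclusion.** The concern holds. Followed literally, the written model does not test the primary hypothesis, the outcome powered at 91% has no stated arm comparison, the response definition cannot classify every ITT subject, and the outcome that decides Phase I is not named. The stated power figures themselves are correct.

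The size depends on how the gap is filled. If either win counts, or the outcome is chosen after the results, the false-positive chance is 7.8–9.1% for an assumed correlation of 0.5–0.8 (9.75% if independent). If both must win, it is 0.9–2.2% (0.25%), and power under the Section 7.1 effects is 87–89% (85%). Under those effects the two tests disagree in 7–11% of trials (14%). If one outcome is fixed in advance, the error is 5%. The plan commits to none of these. The change should be made before unblinding.

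**What to change.** In Section 7.2, the synopsis and Section 3.2.1:

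- Name one primary outcome at the post-30 assessment (the sponsor's choice). Test the other only if the first is significant, each at two-sided 0.05, in the Section 7.3 ITT population with the Section 7.1 LOCF rule.
- Binary outcome: logistic regression of response at post-30, one record per subject, with treatment arm in the model. Gender stays secondary.
- CDRS-R: compare arms at post-30, either on raw change as powered or, preferably, by ANCOVA with arm and baseline CDRS-R, which is already collected. In large samples ANCOVA does not increase the variance relative to raw change; how much it gains depends on values the documents do not give.
- Write one analysis definition under which every ITT subject is a responder or a nonresponder, including a subject with no post-baseline rating. Reconcile it with Sections 3.1, 6.3 and 7.1, and say how remission differs from response. This concerns the analysis only, not allocation to Phase II.
- Label the other scales and the session 10 and 20 results as secondary, and state what the Bonferroni and Tukey sentences apply to. The single Phase I arm comparison needs neither.

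Cost: wording only, with no new data and no change in sample size. The first outcome in the sequence keeps its stated power (91% for CDRS-R change; 94% for response under the Section 7.1 definition). Only one result can be called primary, and the second supports no confirmatory claim if the first fails. If CGI-S is kept in the response definition, the 94% must be rechecked, because Section 7.1 set it for CDRS-R and CGI-I. A subject with CDRS-R <28, CGI-I ≤2 and CGI-S ≥3 would then not be an analysis responder but would enter the Phase II responder cohort. That mismatch already exists between Sections 7.2 and 3.1 and should be acknowledged in the text.

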Subject Participation Duration	Phase I (Randomized, Blinded): 6-8 weeks (Active rTMS vs. Sham) Phase II (Non-Randomized, Open-label): Acute Treatment (Arm 1) vs. Maintenance Treatment (Arm 2) Arm 1: 6-8 weeks of open-label acute treatment (for Phase I treatment nonresponders) Arm 2: 12 months of open-label, bi-weekly maintenance treatment (for Phase I treatment responders)
Objectives	1) To evaluate the antidepressant effects of daily, active rTMS (when compared with sham treatment) in adolescents meeting criteria for Major Depressive Disorder, single or recurrent episode (Phase I). 2a) To evaluate the benefit of daily, active, open-label rTMS in Phase I nonresponders (Phase II, Arm 1). 2b) To evaluate the benefits of bi-weekly, active, open-label maintenance rTMS treatment for Phase I responders over the course of 12 months post-acute treatment (Phase II, Arm 2). 3*) To evaluate, by proton magnetic resonance spectroscopy (¹ H-MRS) at 3 Tesla (3T), neurometabolic biomarkers at the beginning and end of each study phase. 3a. Define regional specificity [anterior cingulate (AC) and left dorsolateral prefrontal cortex (L-DLPFC)] of cerebral metabolites (i.e. glutamate and glutamine) in adolescent depression. 3b. Study whether specific neurochemical resonances are associated with response, remission, and/or maintenance of improvement of clinical depressive symptoms when rTMS is used to treat adolescent depression.
	*Assessed at MCR site only
Number of Subjects	Phase I: Total of 75 enrolled (38 Active/37 Sham) across both sites (50 at MCR; 25 at MUSC) Phase II: All treatment responders and nonresponders will be offered qualified follow-up treatments based on Phase I outcomes.
Diagnosis and Main Inclusion Criteria	Diagnosis of Major Depressive Disorder, single or recurrent, antidepressant treatment-resistant
Study Device	NeuroStar™ TMS System in XPLOR® research configuration

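### The only efficacy model in the plan has no active-versus-sham term, so as written it cannot test primary hypothesis 1; the powered CDRS-R change has no named test

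*Combined protocol and SAP*

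**What the plan says.** **The question.** Objective 1 in the Study Summary is "To evaluate the antidepressant effects of daily, active rTMS (when compared with sham treatment"). Primary hypothesis 1 in 7.2 is that adolescents on active rTMS "will have significant mood improvement when compared to sham treatment".

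**The model.** Section 7.2 assesses response against nonresponse, for both phases, by logistic regression with "independent variables of treatment number (i.e. #10 vs. #20 vs. #30) and gender (male vs. female"). The Study Summary repeats it under "Statistical analysis plan for objectives 1, 2a, 2b": a "logistic regression model with independent variables of treatment number (i.e. #10 vs. #20 vs. #30) and gender (male vs. female"). Section 7.2 then adds: "The primary analysis will not adjust for gender". Its reason is that the gender mix should be alike in the two arms.

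**The sample size.** Section 7.1 powers active against sham after the thirtieth session, two-sided at 0.05, in two forms: response on a CDRS-R and CGI-I cutoff (65% against 25%), and raw CDRS-R change (difference 8.0, SD 10.0). It names LOCF for the primary analysis. Section 7.3 sets the intention-to-treat population.

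**Other tests named in 7.2.** There is an exact test for adverse events, and there are t-tests and analysis of covariance for the spectroscopy hypotheses at one site. There is also a multiple-comparison passage that begins "Statistically significant differences on overall comparisons will be explored using multiple pairwise comparisons".

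**The concern.** A test of a randomised treatment effect needs the randomised arm in the model, or a direct comparison of the arms. The stated model has neither. It can say whether response differs between sessions 10, 20 and 30, and between males and females, with both arms pooled. It cannot say whether active differs from sham.

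The main result of the trial would then rest on choices made outside the plan: how arm enters, whether one visit or three are used and how repeated visits on a subject are handled, how CDRS-R change is tested, and which of the two analyses decides the outcome. Those choices should be fixed before the blind is broken.

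**Working it through.** **1. Does the stated model carry the arm effect?** Its predictors are session number and, secondarily, gender. The text defines treatment number as session 10, 20 or 30, so it cannot be read as arm. Because arm enters nowhere, permuting the arm labels leaves every coefficient and p-value unchanged. This is a logical point and needs no simulation.

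**2. Does other text supply the arm test?**

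| Text | Scope | Supplies it? |
|---|---|---|
| Exact test (7.2) | Adverse events | No |
| t-tests, analysis of covariance (7.2, Summary) | Spectroscopy, one site | No |
| Bonferroni and Tukey sentences (7.2) | Follow-up to an unnamed overall test; no endpoint given, and two arms make only one pair | No |
| LOCF (7.1), ITT (7.3) | Missing data and population | No |

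None of these names a test for CDRS-R change either.

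**3. Timepoints.** Section 7.1 powers one comparison, after session 30. The model in 7.2 enters three sessions per subject and does not mention within-subject correlation. The two sections disagree.

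**4. Response definition.** The powered endpoint in 7.1 uses CDRS-R and CGI-I. Section 7.2 also requires CGI-S of 2 or less. In addition, 7.2 defines nonresponse as CDRS-R of at least 28 together with CGI-I of at least 3. A subject with CDRS-R 30 and CGI-I 2 therefore meets neither definition and has no code.

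**5. Which test do 7.1's power figures assume?** Inputs from 7.1: p1 = 0.65, p2 = 0.25, difference 8.0, SD 10.0, two-sided 0.05, n = 35 per group (25 for completers).

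*Response, normal approximation with pooled variance:* power = Φ{[|p1−p2| − 1.96·√(2p̄(1−p̄)/n)] / √([p1(1−p1)+p2(1−p2)]/n)}, with p̄ = 0.45.
- n = 35: (0.400 − 1.96 × 0.1189) / 0.1089 = 1.533, power 93.7% (stated 94%).
- n = 25: (0.400 − 1.96 × 0.1407) / 0.1288 = 0.964, power 83.2% (stated 83%).

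*CDRS-R change, two-sample t-test:* noncentrality = (8/10)·√(n/2).
- n = 35: 3.347, power 91.0% by noncentral t (stated 91%).
- n = 25: 2.828, power 79.1% by noncentral t, 80.7% by normal approximation (stated 80%).

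The stated figures reproduce as direct two-arm comparisons. The sample size therefore rests on tests that 7.2 does not write down.

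**6. Power once arm is the tested term.** Exact enumeration for response at 35 per group:

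| Test of arm at session 30 | Power, 65% vs 25% |
|---|---|
| Logistic regression, likelihood ratio | 93.3% |
| Chi-square, uncorrected | 92.8% |
| Logistic regression, Wald | 92.5% |
| Fisher exact | 89.0% |

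With both arms at 45%, the chi-square rejects in 4.4% of trials. For CDRS-R change the t-test gives 91.0%, as in step 5.

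**7. Why rank matters.** The plan sets 0.05 for every test. If success on either endpoint counted, and the two were independent, the chance of a false positive would be 1 − 0.95² = 9.75%. They share the CDRS-R, so the true figure would probably be lower. The plan does not say that either would count; it leaves the matter open.

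**The case against.** The best reply is that the arm comparison is obvious. Section 7.1 gives the contrast, timepoint, both outcome forms, significance level and LOCF, and 7.3 gives the population. Section 7.2 tabulates the treatment groups to find "potential confounding variables to be used as covariates in sensitivity analyses". Its reason for leaving gender out makes sense only if arms are being compared. The model sentence also covers Phase II, which has no sham arm, so arm could not sit in a common list of terms. On this view the sentence is a compressed covariate list.

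All of that stands as evidence of intent, and it narrows the gap. The timepoint is a conflict between 7.1 and 7.2, not a silence, and for CDRS-R change the contrast is given and only the test is missing. It does not cure the defect. The same two terms appear in both places where the model is stated, the Summary applies them to objective 1 by number, and no sentence writes the arm test.

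Two stronger readings are tempting, and the documents do not support them.
- A reader might remove gender from the model and infer a primary analysis on session number alone. The reason given for removing gender points to an arm comparison, so this does not follow.
- A reader might infer from the visit schedule that a dropout before session 10 has no planned CGI-I. Table 4 (footnote g) and 6.2.8 schedule it at early withdrawal. A code for missing ratings is needed only for subjects who also miss that visit.

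**Conclusion.** The point holds and must be fixed. The efficacy model as written does not test primary hypothesis 1, and one of the two powered endpoints has no named analysis. The size of the defect is categorical: the active-versus-sham effect is not estimated at all.

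A reader might go on to infer that the trial is too small or that its power statement is wrong. The check does not support that. With arm as the tested term, 35 per group gives about 93% for response (89% with Fisher) and 91% for CDRS-R change. These figures rest on 7.1's own assumptions: 65% against 25%, a difference of 8.0 with SD 10.0, and no allowance for attrition under LOCF. The response figure also belongs to the endpoint as 7.1 defines it. The documents give no rates for the definition in 7.2 that adds CGI-S.

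**What to change.** In 7.2 and the Study Summary, for Phase I efficacy:

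1. Make arm the tested term at post-treatment 30, with one record per ITT subject under the existing LOCF rule; for example, logistic regression of response on arm. If all three visits are modelled, include arm, visit and arm-by-visit, account for within-subject correlation, and test the arm contrast at session 30.
2. Name a two-arm test of CDRS-R change at session 30; for example, analysis of covariance on baseline CDRS-R.
3. State which of the two analyses is primary.
4. Reconcile the response definitions in 7.1 and 7.2, use one throughout, and code every subject as met or not met. State the code for a subject with no post-baseline rating, such as a dropout who misses the early-withdrawal assessment.

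Phase II can keep its descriptive analysis under a separate sentence.

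The cost is wording only: no new data, no change in N, and no change to the LOCF, ITT, significance-level or gender rules. The amendment should be dated before unblinding.
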